4.2.2 OLAPARIB

4.2.2.1 COMBINATION WITH RADIATION

Pre-clinical work found that when comparing subablative hypofractionated radiation versus ablative single fraction SBRT, a dose of >10 to 12Gy resulted in increased immunosuppression due to upregulation of DNA exonuclease Trex1, which leads to decreased production of cyclic GMP-AMP and subsequently, decreased immune gene transcription [Vanpouille-Box C et al., 2017]. In addition, doses >10 Gy caused vascular damage which led to reduced effector T-cell recruitment to the tumor [Park HJ et al., 2012]. In contrast, a moderate subablative dose of 8 Gy x 3 has been shown to increase tumor immunogenicity and increase of abscopal effect [Ko EC et al., 2018; Park HJ et al., 2012]. A phase 1 dose-escalation study evaluated five different dose levels of SBRT with neoadjuvant chemotherapy in patients with HER2 negative breast cancer. The pathological complete response rate (pCR) was 36%, and none were seen in the first 2 dose levels and did not increase with dose escalation beyond dose level 3 (25.5 Gy over 3 consecutive days). This study suggested that 25.5 Gy is the optimal dose for preoperative SBRT to elicit tumor responses[Bondiau PY et al., 2013].

4.2.2.2 COMBINATION WITH PEMBROLIZUMAB

A phase I study evaluating durvalumab with olaparib in recurrent ovarian, cervical and triple negative breast cancers determined the RP2D as olaparib 300mg twice daily [Lee et al., 2017]

4.3 RADIATION DETAILS

The treating radiation oncologist will select 1 site of disease (metastatic or primary) to target with radiation. Sites of disease planned to be biopsied should not be radiated.

Guidance on choosing site for irradiation:

- A single site (metastasis or primary lesion) will be chosen for irradiation
- Disease site planned to be biopsied should not be radiated
- There should be a measurable lesion apart from the irradiated lesion
- A disease site causing clinical symptoms that would benefit from palliative radiation should be prioritized (e.g. pain, obstruction, bleeding, etc). If there are no areas causing significant clinical symptoms, radiation oncology can choose the disease site for radiation per their discretion.

Simulation and treatment may be performed with the patient in the supine or prone position with appropriate immobilization devices for the specific tumor location at the discretion of the treating radiation oncologist. The CT should extend cephalad ≥ 5 cm above the tumor to be treated, and ≥ 5 cm caudad. External skin localizing marks, which may include permanent tattoos, are recommended for radiation daily localization and set-up accuracy. The radiation oncologist will contour a gross tumor volume (GTV) and internal target volume (ITV) when 4D CT simulation is obtained. No additional expansion will be added for a clinical target volume (CTV) in most cases. GTV (or ITV) to planning target volume (PTV) expansion of 3-7 mm will be applied and can be modified around organs at risk at the discretion of the treating radiation oncologist. Dose should be prescribed to the PTV. Greater than 95% of the PTV should be covered by greater than 95% of the prescription dose, but it is allowable to compromise PTV coverage to meet OAR constraints. Maximum point dose within the PTV may up to 130% of the prescribed dose, but effort should be made to minimize hot spots $>110\%$ of the prescribed dose that fall outside the GTV. Intratumoral fiducial markers and/or respiratory gating techniques are not required, but can be utilized at the discretion of the treating radiation oncologist, when determined to be appropriate and technically feasible. 3D conformal or Intensity Modulated Radiation Therapy (IMRT) techniques are acceptable for treatment planning, although IMRT is preferred. Volumetric Modulated Arc Therapy (VMAT) and static IMRT are both acceptable. Image guidance modality and frequency is at the discretion of the treating radiation oncologist.

All patients will be treated with 5 Gy per fraction for a total of 5 fractions totaling 25 Gy. Radiation treatment will be delivered daily and to be completed within 2 weeks in case course falls over weekend or there are other logistical issues (i.e. machine downtime issues).

Protocol radiation dosing regimen is outlined in the table below:

Regimen [†]	Dose per fraction	Number of fractions	Total dose	EQD2 ₁₀ /EQD2 ₃
A	5 Gy	5	25 Gy	31.25/40

Organ at risk dose constraints are provided below and all provided constraints must be met. Constraints have been adapted from institutional dose constraints, the widely accepted and utilized Timmerman dose constraints, and appropriate clinical studies when applicable. Most constraints have been adapted to be more conservative. No constraints have been made more lenient for this study.

5-fraction OAR constraints

OAR	Volumetric constraint(s) (if applicable)	Max point dose (if applicable)
Brachial plexus	-	26.0 Gy
Spinal cord*	V15<0.35 cc	22.5 Gy
Cauda equina	V21<5 cc	25.5 Gy
Esophagus**	V17.7<5 cc	25.2 Gy
Heart	V24<15 cc	30.0 Gy
Great vessels	V39<10 cc	45.0 Gy
Large airways	V25.8<5 cc	30.0 Gy
Chest wall	V30<30 cc	-
Lung (ipsilateral-ITV)	Mean<9 Gy	-
Lung (total-ITV)	V11<35%	-
Liver	At least 700 cc < 12 Gy	-
Stomach	V30<1 cc	33.0 Gy
Duodenum	V30<1 cc V20<5 cc	33.0 Gy
Small bowel (bowel bag)	V20<10 cc	27.0 Gy
Large bowel and rectum	V20<5 cc	30.0 Gy
Kidney (each hilum)	V19.5<15 cc	-
Kidney (bilateral cortex)	V14.7<1/3 volume	-
Bladder	V17<15 cc	33.0 Gy
Femoral heads	V24<10 cc	-

* For spine SBRT, MR or CT-myelogram imaging is required to define the cord for OAR avoidance.

**Avoid circumferential irradiation

4.4 END OF STUDY DEFINITION

The study will be completed once 26 patients are evaluable for the primary endpoint, and the last patient enrolled has been evaluated for objective response rate (ORR). Evaluable is defined as patients who have received at least 1 dose of the treatment, SBRT + Olaparib and Olaparib + Pembrolizumab, and have had baseline imaging.

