University of Colorado Hospital (UCHealth Metro and Highlands Ranch Hospital)
 Memorial Hospital (UCHealth South)

Description of Study Intervention:

Concurrent SBRT with Olaparib followed by combination Olaparib and Pembrolizumab

[figure not shown]
Study Duration:

Enrollment will last approximately 3 years. Total length of study is 4 years. Enrollment is anticipated at 8 per year

Participant Duration:

1 year from study initiation

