^h Tumor imaging is strongly preferred to be acquired by computed tomography (CT). For the abdomen and pelvis, contrast-enhanced magnetic resonance imaging (MRI) may be used when CT with iodinated contrast is contraindicated, or when local practice mandates it. MRI is the strongly preferred modality for imaging the brain. The same imaging technique regarding modality, ideally the same scanner, and the use of contrast should be used in a participant throughout the study to optimize the reproducibility of the assessment of existing and new tumor burden and improve the accuracy of the assessment of response or progression based on imaging.

ⁱ Evaluation of ECOG at screening is to be performed within 14 days prior to the date of treatment.

^j Medical history will include all active conditions and any condition diagnosed within the prior 10 years that are considered to be clinically significant by the Investigator

^k The investigator or qualified designee will review all new anti-neoplastic therapy initiated after the last dose of trial treatment. If a participant initiates a new anti-cancer therapy within 30 days after the last dose of trial treatment, the 30 day Safety Follow-up visit must occur before the first dose of the new therapy. Once new anti-cancer therapy has been initiated the participant will move into survival follow-up. If the post-trial visit occurs less than 30 days after the last dose of study treatment, a subsequent follow-up phone call should be made at 30 days post the last dose of study treatment to determine if any adverse events have occurred since the post-trial clinic visit

^l ECGs are required within 7 days prior to starting study treatment

^m Laboratory tests for screening or entry into the Second Course Phase should be performed within 10 days prior to the first dose of treatment. After Cycle 1, pre-dose laboratory procedures can be conducted up to 72 hours prior to dosing. Results must be reviewed by the investigator or qualified designee and found to be acceptable prior to each dose of trial treatment.

ⁿ In participants who discontinue study treatment without documented disease progression, every effort should be made to continue monitoring their disease status by tumor imaging using the same imaging schedule used while on study treatment (every 12 weeks \pm 7 days) until the start of a new anticancer treatment, disease progression, pregnancy, death, withdrawal of consent, or the end of the study, whichever occurs first.

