7.2 PARTICIPANT DISCONTINUATION/WITHDRAWAL FROM STUDY

Participants are free to withdraw from participation in the study at any time upon request.

In addition, the investigator has the right to withdraw a patient from the study at any time should any untoward effect occur. In addition, a participant may be discontinued from study treatment by the investigator or the Sponsor if study treatment is inappropriate, the trial plan is violated, or for administrative and/or other safety reasons. Specific details regarding procedures to be performed at study treatment discontinuation are provided in Section 8.1.4.1.

A participant must be discontinued from study treatment but continue to be monitored in the study and moved to survival follow-up for any of the following reasons:

- The participant or participant's legally acceptable representative requests to discontinue study treatment
- Confirmed radiographic disease progression outlined in Section 8.1.2.6
- Any progression or recurrence of any malignancy, or any occurrence of another malignancy that requires active treatment

Note: Participants with basal cell carcinoma of the skin, squamous cell carcinoma of the skin, or carcinoma in situ (excluding carcinoma in situ of the bladder) who have undergone potentially curative resection do not have to discontinue study intervention.

- Unacceptable adverse experiences as described in Appendix 5 and Appendix 6.
- The participant has a medical condition or personal circumstance which, in the opinion of the treating investigator and/or sponsor, placed the participant at unnecessary risk from continued administration of study treatment.
- Sponsor-Investigator determines it is in the best interest of the patient
- Patient non-compliance with the study treatment or procedure as determined by the treating investigator
- The participant has a confirmed positive serum pregnancy test
- Recurrent Grade 2 pneumonitis
- Discontinuation of treatment may be considered for participants who have attained a confirmed complete response (CR) and have been treated for at least 8 cycles (at least 24 weeks), receiving 2 cycles of the combination including 2 doses of pembrolizumab and at least 80% of the planned doses of olaparib and pembrolizumab beyond the date when the initial CR was declared. These participants may be eligible for second course treatment described in Appendix 7.
- Administrative reasons

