8.1.4.3 POST-TREATMENT VISITS

Safety Follow-Up Visit

The mandatory Safety Follow-Up Visit should be conducted approximately 30 days after the last dose of study treatment or before the initiation of a new anti-cancer treatment, whichever comes first. If the post-trial visit occurs less than 30 days after the last dose of study treatment, a subsequent follow-up phone call should be made at 30 days post the last dose of study treatment to determine if any adverse events have occurred since the post-trial clinic visit. All AEs that occur prior to the Safety Follow-Up Visit should be recorded. Participants with an AE of Grade > 1 will be followed until the resolution of the AE to Grade 0-1 or until the beginning of a new anti-cancer therapy, whichever occurs first. SAEs that occur within 90 days of the end of treatment or before initiation of a new anti-cancer treatment will also be followed and recorded. Participants who are eligible for retreatment/crossover with pembrolizumab (as described in Appendix 7) may have up to two safety follow-up visits, one after the Initial Treatment Period and one after the Second Course Treatment.

Follow-Up Visits

Participants who discontinue study treatment for a reason other than disease progression will move into the Follow-Up Phase and should be assessed every 12 weeks (42 ± 7 days) by radiologic imaging to monitor disease status. Every effort should be made to collect information regarding disease status until the start of new anti-cancer therapy, disease progression, death, end of the study or if the participant begins retreatment with pembrolizumab as detailed in Appendix 7. Information regarding post-study anti-cancer treatment will be collected if new treatment is initiated.

Participants who are eligible to receive retreatment with pembrolizumab according to the criteria in Appendix 7 will move from the follow-up phase to the Second Course Phase when they experience disease progression.

Survival Follow up

Participants who experience confirmed disease progression or start a new anticancer therapy, will move into the Survival Follow-Up Phase and should be contacted by telephone every 12 weeks to assess for survival status until death, withdrawal of consent, or the end of the trial, whichever occurs first. Patients will be followed for 5 years for survival.

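### Closing the study at the last response evaluation is incompatible with the stated 5 years of survival follow-up, and the imaging rules for patients who stop without progression conflict

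*Combined protocol and SAP*

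**What the plan says.** **Closure and follow-up length**

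- Section 4.4: "The study will be completed once 26 patients are evaluable for the primary endpoint, and the last patient enrolled has been evaluated for" objective response.
- Section 8.1.4.3: telephone contact every 12 weeks to "assess for survival status until death, withdrawal of consent, or the end of the trial, whichever occurs first". The next sentence reads "Patients will be followed for 5 years for survival". Footnote r of the schedule of events (1.3) says the same.
- Synopsis (1.1): "Enrollment will last approximately 3 years. Total length of study is 4 years. Enrollment is anticipated at 8 per year". Participant duration is "1 year from study initiation".

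**Patients who stop treatment without progression**

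- Section 8.1.4.3: they "should be assessed every 12 weeks (42" ± 7 days).
- Section 1.3, footnote n: their imaging follows "the same imaging schedule used while on study treatment (every 12 weeks" ± 7 days). The on-treatment interval in section 8.1.2.6.1 is 9 weeks (63 days).
- Section 8.1.2.6.2 and footnote r: every 12 weeks, with no figure in days.
- Section 7.2: patients must stop treatment but "continue to be monitored in the study and moved to survival follow-up for any of the following reasons". The list includes unacceptable adverse experiences and discontinuation after confirmed complete response.
- Section 8.1.4.1 sends complete responders who stop to the Follow-Up Period. Section 8.1.4.3 reserves survival follow-up for confirmed progression or new anticancer therapy.

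Section 9.4.3 plans Kaplan-Meier curves and medians for OS, PFS and DoR, without formal tests.

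**The concern.** Survival contact ends with the trial, and section 4.4 ends the trial at a response evaluation. The stated 5 years then cannot be reached, and the patients enrolled last contribute very little OS, PFS or DoR follow-up. The synopsis durations do not resolve this, because 4 years in total is also less than 5 years for any one patient.

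The second problem is separate. A patient who stops for toxicity, or after a complete response, has not progressed, so PFS and DoR still depend on later scans. Sites can find three different intervals in the text. In section 7.2 they can also find an instruction that moves these patients to a phase with telephone contact only. Stopping scans at toxicity may be related to prognosis, and stopping them in complete responders loses the DoR information they carry. Sections 9.1 and 9.4.3 give no censoring rule for this situation.

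**Working it through.** **1. The synopsis's own durations.** 26 patients at 8 per year take 26/8 = 3.25 years (39 months), against the stated approximately 3 years (36 months). Three years of enrolment plus 1 year per participant gives the stated 4 years. That total therefore leaves no room for 5 years of survival contact.

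**2. Time of closure under section 4.4.** Let A be the accrual period and t the time from last entry to the last response read. The documents do not define t. The first scan is at 9 weeks (about 2.1 months), and confirmation at least 4 weeks later gives 13 weeks (about 3.0 months). I take t = 2 to 4 months. With uniform entry:

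- maximum potential follow-up = A + t
- share with under 12 months = (12 − t)/A
- share with under 24 months = (24 − t)/A

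| Rule | A (months) | t (months) | Closure (months) | Under 12 months | Under 24 months |
|---|---|---|---|---|---|
| Section 4.4 | 36 | 2 | 38 | 10/36 = 28% | 22/36 = 61% |
| Section 4.4 | 36 | 4 | 40 | 8/36 = 22% | 20/36 = 56% |
| Section 4.4 | 39 | 2 | 41 | 10/39 = 26% | 22/39 = 56% |
| Section 4.4 | 39 | 4 | 43 | 8/39 = 21% | 20/39 = 51% |
| 4-year length | 36 | 12 | 48 | 0/36 = 0% | 12/36 = 33% |
| 4-year length | 39 | 9 | 48 | 3/39 = 8% | 15/39 = 38% |

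Every closure time is below 60 months. Reading response as late as week 24 (5.5 months) moves closure only to 41.5–44.5 months. Enrolling the maximum of 32 at 8 per year (48 months), with t up to 4 months, gives at most 52.

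**3. DoR in the last entrants.** A first response at week 9, with closure at week 9 to 13, leaves 0 to 4 weeks of DoR follow-up.

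**4. Can median OS still be estimated?** Assume exponential survival with median m, 26 evenly spaced entries, A = 36–39 months and t = 9–13 weeks. Expected deaths at closure are the sum over patients of 1 − exp(−ln 2 × follow-up/m). Using medians quoted in section 2.2 as illustrations:

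- m = 5.3 months: about 22 of 26
- m = 11.4 months: about 17 to 18 of 26
- m = 14.4 months: about 15 to 16 of 26

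More than half the patients are expected to have died in each case.

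**5. Follow-up needed for 5 years in every patient.** 3 + 5 = 8 years, or 3.25 + 5 = 8.25 years.

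**6. Off-treatment intervals.** 12 weeks is 12 × 7 = 84 days. 42 days is 6 weeks. The on-treatment schedule is 63 days. A simulation assumed exponential progression with median PFS of 12 to 20 weeks, and gave 10–30% of patients a stopping time uniform over 26 weeks. Moving the off-treatment interval from 6 to 12 weeks changed mean observed PFS by about 0.3 to 0.6 week.

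**7. Section 7.2 against the rest.** Sections 8.1.2.6.2, 8.1.4.1 and 8.1.4.3 and footnotes n and r all keep patients who stop without progression under disease follow-up. Appendix 7 requires radiographic progression after stopping for the second course, which also presupposes scans. Section 7.2 alone points the other way.

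**The case against.** Several counter-arguments have force.

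- **The 5 years may be a cap.** The sentence before it limits contact to the end of the trial if that comes first. That reading is possible, but no patient could reach the cap, so the text still needs correcting.
- **The endpoints are descriptive.** Section 3 says the study is not powered to compare OS or PFS with other regimens, no 5-year survival rate is an endpoint, and section 6.1 schedules OS and PFS looks at 12 and 24 months. This stands and limits the consequence.
- **The 42-day figure is isolated.** The Q12W schedule column, footnotes n and r, and sections 8.1.2.6.2 and 8.1.4.3 all give 12 weeks, and 42 appears once in parentheses. The interval conflict touches only patients who stop without progression, and its likely effect on PFS is small. This also stands.
- **Section 7.2 is a lead-in.** It also says patients continue to be monitored, and the more specific sections provide scans.

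A reader might infer that valid PFS and DoR cannot be delivered, or that patients leaving for toxicity will be censored without scans. The documents support neither. Closure at a trigger unrelated to a patient's own prognosis is administrative censoring, which Kaplan-Meier handles. Loss of scans after toxicity arises only if a site follows section 7.2 over the more specific passages.

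**Conclusion.** The contradictions are in current operative text and should be corrected.

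**Closure.** Under section 4.4 the study would end about 38 to 43 months after first entry, and under the synopsis at 48 months, so nobody reaches 5 years. Potential follow-up is under 12 months for about 21–28% of patients and under 24 months for 51–61%. Under the 4-year length these shares are 0–8% and 33–38%. The figures assume uniform accrual over 36 to 39 months and, for section 4.4, a last read 2 to 4 months after last entry. The cost is lost follow-up and precision for OS, PFS and DoR, mainly in late entrants and in the tails of the curves. The estimates remain valid and median OS should remain estimable.

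**Imaging after stopping without progression.** The interval is stated inconsistently, with a small expected effect on PFS. The section 7.2 conflict matters more: followed literally, it would stop scans in non-progressing patients, including complete responders, with possibly informative censoring of PFS and DoR. Its size cannot be computed, because the documents do not give the number of such patients.

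The primary ORR test is unaffected.

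**What to change.** 1. In section 4.4, rename the present rule the primary-analysis cut-off, say what counts as evaluated for response, and define the end of study separately as completion of survival follow-up.
2. Make the synopsis, footnote r and section 8.1.4.3 state one follow-up length. The sponsor can keep 5 years, which means about 8 to 8.25 years in total if every patient is to have it, or restate the 5-year figure to match the intended study length.
3. Reconcile footnote n, section 8.1.2.6.2 and section 8.1.4.3 to one off-treatment imaging interval, stated in days.
4. Reconcile section 7.2 with sections 8.1.2.6.2, 8.1.4.1 and 8.1.4.3 on which patients move to follow-up without scans.

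Items 1, 3 and 4 are wording changes, and telephone contact and off-treatment scans are already planned. The real cost lies in item 2. Keeping 5 years roughly doubles the stated study length and also lengthens the time the second course is available, since Appendix 7 offers it only while the study remains open. Restating the figure avoids that cost but gives up long-term survival data.

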9.2 SAMPLE SIZE DETERMINATION

This is a one arm single-stage Phase II clinical trial. The null hypothesis that the ORR is 0.25 will be tested against the one-sided alternative that the ORR is 0.45. Total of 26 patients yields a

type I error rate of 0.1 when the null hypothesis is true and power of 0.8 when the alternative hypothesis is true.

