9.3 POPULATION FOR ANALYSES

All eligible patients who has received any level of the target treatment will be included in the analyses for all preliminary, secondary and safety analysis except for the duration of response analysis. The analysis for duration of response will only include the patients who has responded.

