9.4.2 ANALYSIS OF THE PRIMARY EFFICACY ENDPOINT(S)

One-sided proportion test will be conducted for the ORR, with significant level 0.1. The cumulative frequency, estimated proportion and the exact 95% confidence interval will be reported.

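### Sections 4.4 and 9.3 give different denominators for the primary ORR; if the section 4.4 set is used for the test, ORR is biased upward and the 0.1 type I error is no longer assured

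*Combined protocol and SAP*

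**What the plan says.** Section 4.4 (End of study definition) sets the finishing point: "The study will be completed once 26 patients are evaluable for the primary endpoint", with the last enrolled patient assessed for ORR. It adds: "Evaluable is defined as patients who have received at least 1 dose of the treatment, SBRT + Olaparib and Olaparib + Pembrolizumab", and also requires baseline imaging. By section 6.1, pembrolizumab is first given on Day 1 of Cycle 2, so on its natural reading this set contains only patients who started Cycle 2.

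Section 9.3 (Population for analyses) is wider: "All eligible patients who has received any level of the target treatment will be included in the analyses for all preliminary, secondary and safety analysis", with duration of response as the only exception. *Preliminary* there is probably a slip for *primary*. Read literally, section 9.3 would name no population for the primary endpoint.

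Section 9.2 gives the design: "The null hypothesis that the ORR is 0.25 will be tested against the one-sided alternative that the ORR is 0.45". The 26 patients are said to give a "type I error rate of 0.1 when the null hypothesis is true and power of 0.8 when the alternative hypothesis is true". Section 9.4.2 adds: "One-sided proportion test will be conducted for the ORR, with significant level 0.1". Neither section says which set the 26, the null rate or the test refers to. Neither names the test or gives a critical number of responders. No section says how to count a patient who has no post-baseline scan.

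**The concern.** The two sets differ mainly by patients who received some SBRT or olaparib but did not start Cycle 2, whether through death, toxicity, clinical progression or withdrawal. They are not a random subset. The first on-study scan is planned at 9 weeks and a response should be confirmed at least 4 weeks later (section 8.1.2.6.1), so these patients are unlikely to be recorded as responders. Induction is part of the combined therapy whose efficacy is the primary objective. Leaving them out of the denominator turns the ORR into a rate conditional on getting through induction, which is higher than the rate for the regimen as given.

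The ORR test is the only formal test in the plan (section 9.4.3 excludes tests of secondary endpoints). With 26 patients, a change of one to three in the denominator can change its result. If the set is not fixed before response data are seen, choosing it can amount to choosing the answer.

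**Working it through.** **Inputs.** p0 = 0.25, p1 = 0.45, one-sided alpha 0.1, power 0.8, n = 26 (section 9.2); enrolment cap 32, stated to allow for screen failures (section 1.1); planned enrolment 26 (section 6.1). The documents give no Cycle 1 loss rate, so a range is shown.

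**Step 1: the plan's own figure.** P(X ≥ r | n, p) = Σ C(n,x) p^x (1−p)^(n−x), summed from x = r to n.

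- r = 9, n = 26: P(X ≥ 9 | 0.25) = 0.180, too high.
- r = 10, n = 26: P(X ≥ 10 | 0.25) = 0.0909; P(X ≥ 10 | 0.45) = 0.806.
- n = 25, r = 10: 0.071 and 0.758, so power is short.

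The exact binomial design therefore reproduces n = 26 with success at 10 or more responders. The attained type I error is 0.091; the stated 0.1 is its ceiling.

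**Step 2: section 4.4 set, with lost patients replaced until 26 are evaluable.** Assume that the true ORR among all treated patients is 0.25 and that the k patients lost before Cycle 2 do not respond. The ORR among evaluable patients is then 0.25 × (26 + k)/26, and the rejection probability is P(X ≥ 10 | 26, that rate). The last column tests the same 10 responders against all treated patients, P(X ≥ 10 | 26 + k, 0.25).

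| k replaced | Treated | ORR among evaluable | Rejection probability | p for 10 responders among all treated |
|---|---|---|---|---|
| 0 | 26 | 0.2500 | 0.091 | 0.091 |
| 1 | 27 | 0.2596 | 0.112 | 0.113 |
| 2 | 28 | 0.2692 | 0.135 | 0.138 |
| 3 | 29 | 0.2788 | 0.162 | 0.166 |
| 4 | 30 | 0.2885 | 0.191 | 0.197 |
| 6 | 32 | 0.3077 | 0.257 | 0.263 |

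The row for 6 is an extreme, because it uses the whole margin up to the cap with no screen failures. In terms of a loss fraction d, the evaluable ORR is 0.25/(1 − d), and the rejection probability passes 0.10 at d of about 1.7%.

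The row for 3 shows the practical conflict: 10/26 evaluable is 38.5% with p = 0.091, significant at 0.1; the same 10 responders in 29 treated is 34.5% with p = 0.166, not significant.

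**Step 3: section 4.4 set, 26 treated and no replacement.** Dropping 1 or 2 leaves the exact cut-off at 10 and the error at about 0.09. Dropping 3 leaves n = 23 with cut-off 9 (nominal 0.096); at an evaluable ORR of 0.25 × 26/23 = 0.283 the rejection probability is 0.176. For 3 to 6 dropped it is about 0.17 to 0.18.

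**Step 4: section 9.3 set with the exact test.** If enrolment continues until 26 are evaluable, more than 26 may have been treated.

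| Treated n | Cut-off | Type I error | Power at 0.45 |
|---|---|---|---|
| 26 | 10 | 0.091 | 0.806 |
| 27 | 11 | 0.053 | 0.737 |
| 28 | 11 | 0.068 | 0.787 |
| 29 | 11 | 0.086 | 0.829 |
| 30 | 12 | 0.051 | 0.767 |
| 31 | 12 | 0.064 | 0.811 |
| 32 | 12 | 0.080 | 0.849 |

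The type I error stays below 0.1 at every size. Power is below 0.8 at n = 27, 28 and 30.

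**The case against.** The strongest reply is that section 4.4 governs when the study ends and section 9.3 governs who is analysed, and that section 9.3 already keeps everyone treated. On that reading there is no bias, and an exact test holds its level. This is a fair reading, and it limits the point. It does not remove it: section 4.4 ties its definition expressly to the primary endpoint, section 9.3 does not actually use the word *primary*, and section 9.4.4 repeats the both-phases wording for immune evaluability, so the phrase does not look accidental.

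A reader might infer several stronger things that the documents do not support:

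- *The type I error of 0.1 is not held.* It is exceeded only if the section 4.4 set is the test denominator, the 0.25 null refers to all treated patients, and enough patients are lost: more than about 1.7% with replacement, or at least 3 of 26 without. If the null is defined within evaluable patients, the error is 0.091.
- *Everyone who fails in Cycle 1 is removed.* A patient who worsens in Cycle 1 but receives a Cycle 2 dose stays evaluable. The excluded group is those who do not start Cycle 2, and anyone without baseline imaging.
- *Those patients are non-responders by construction.* Scans may be done early if clinically indicated, and patients who stop without progression continue to be imaged every 12 weeks (sections 8.1.2.6.1 and 8.1.2.6.2). Non-response is a plausible assumption, not a certainty.
- *Up to six treated patients will be replaced.* The margin between 26 and 32 is stated to be for screen failures, and no replacement rule is written. Still, requiring 26 evaluable patients implies treating more than 26 if anyone is lost before Cycle 2.
- *The unnamed test inflates the error.* An uncorrected normal-approximation test would have true levels of 0.113, 0.138, 0.106 and 0.128 at n = 27, 28, 30 and 31, but the plan does not name that test. The sample size matches the exact binomial, and at n = 26 the exact and normal tests share the cut-off of 10. Naming the test is a clarification.

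**Conclusion.** The inconsistency is real: the plan gives two denominators for its primary endpoint and does not say which one the test uses. If the section 4.4 set is used, the direction of the bias is upward. The size is conditional. With a true ORR of 25% among all treated patients and no responses among those lost, the false-positive probability rises from 0.091 to 0.112 with one replacement and to 0.191 with four. The actual loss before Cycle 2 cannot be judged from the documents. Confidence is high in the inconsistency and lower in the size of its effect. Because section 9.3 can already be read as including all treated patients, and wording resolves the matter, this should be fixed but is not a fatal flaw in the design.

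**What to change.** - **Sections 4.4 and 9.3:** name one primary population, all eligible patients who start any SBRT or olaparib. Count a patient with no post-baseline response assessment as a non-responder. Replace *preliminary* with *primary* if that is what is meant. Complete accrual at 26 treated patients, without replacement for efficacy. Keep the section 4.4 set as a labelled sensitivity analysis.
- **Section 9.2:** say that the 0.25 null and the 26 patients refer to this population.
- **Section 9.4.2:** name the exact binomial test, with success at 10 or more responders in 26 (type I error 0.091, power 0.806). If more than 26 are treated despite the accrual rule, use at least 11 for n = 27 to 29 and at least 12 for n = 30 to 32, and state that power is then 0.737, 0.787 and 0.767 at n = 27, 28 and 30.

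The cost is a few sentences, settled before response data are seen. The reported ORR may come out slightly less favourable than under the evaluable definition.
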